11.1.6.4. Pharmacokinetic Assessments

Pharmacokinetic assessments to measure plasma concentrations of ETC-1002 and its metabolite ESP15228 will be conducted from 6 mL whole blood samples collected. At the time of sample

collection, the date and time of blood draw and the last 2 doses of study medication will be collected. Pharmacokinetic sample analyses for ETC-1002 and ESP15228 will be conducted by the bioanalytical laboratory.

11.1.6.5. Collection and Assessment of Pharmacokinetic Samples

Pharmacokinetic samples will be collected from patients prior to dose at Week 4 (Visit T2), Week 8 (Visit T3), and Week 12 (Visit T4), dosing time and PK sampling time must be documented, for use in further developing the population PK model.

Plasma concentrations of ETC-1002 and its metabolite (ESP15228) will be determined using validated methods. Plasma PK samples will be labeled with preprinted information, including study number, patient identification number, study day, nominal time of sample collection, matrix, and a text identification (ie, “Plasma PK”). See the study laboratory manual for further instructions.

11.1.6.6. Shipment of Pharmacokinetic Samples

Plasma PK samples will be shipped frozen on dry ice according to instructions provided in the laboratory manual.

11.1.6.7. Total Blood Volume of Clinical Laboratory and Pharmacokinetic Samples

The total number of venipunctures and total volume of whole blood collected during the study will be limited to that needed for safety monitoring, PK, efficacy, and biomarker assessment. Total whole blood volume collected over the study duration is not to exceed approximately 250 mL for each patient.

11.2. Adverse and Serious Adverse Events

11.2.1. Definition of Adverse Events

An AE is any untoward medical occurrence in a clinical investigation patient administered a pharmaceutical product, including control, and which does not necessarily have a causal relationship with treatment.

An AE can be:

- Any unfavorable and unintended sign (including an abnormal laboratory finding), symptom, or disease temporally associated with the use of a medicinal product, whether or not considered related to the medicinal product
- Any new disease or exacerbation of an existing disease
- Any deterioration in nonprotocol-required measurements of laboratory value or other clinical test (eg, ECG or x-ray) that results in symptoms, a change in treatment, or discontinuation from study drug
- TEAEs are defined as AEs that begin or worsen after the first dose of study drug
- Adverse drug reaction (ADR; see [Section 11.2.2](#))

11.2.2. Adverse Drug Reaction

All noxious and unintended responses to a medicinal product related to any dose should be considered an ADR. “Responses” to a medicinal product means that a causal relationship between a medicinal product and an AE is at least a reasonable possibility (ie, the relationship cannot be ruled out).

An unexpected ADR is defined as an adverse reaction, the nature or severity of which is not consistent with the applicable product information (eg, IB for an unapproved investigational product or package insert/summary of product characteristics for an approved product).

11.2.3. Reporting

All AEs occurring during the course of the study (starting from signing informed consent to study completion or discontinuation) will be collected on the AE eCRF. Patients should be instructed to report any AE that they experience through 30 days following the last dose of IMP to the investigator. Any SAE that occurs within 30 days following the last study visit should be reported to the Sponsor per [Section 11.3](#). Beginning with Visit S2 (Week -4), investigators should make an assessment for AEs at each visit and record the event on the appropriate AE eCRF.

Wherever possible, a specific disease or syndrome rather than individual associated signs and symptoms should be identified by the investigator and recorded on the eCRF. However, if an observed or reported sign or symptom is not considered a component of a specific disease or syndrome by the investigator, it should be recorded as a separate AE on the eCRF. Additionally, the condition that led to a medical or surgical procedure (eg, surgery, endoscopy, tooth extraction, transfusion) should be recorded as an AE, not the procedure.

Any medical condition already present at screening or baseline should not be reported as an AE unless the medical condition or signs or symptoms present at baseline change in severity or seriousness at any time during the study. In this case, it should be reported as an AE.

Clinically significant abnormal laboratory or other examination (eg, ECG) findings that are detected during the study or are present at baseline and significantly worsen during the study should be reported as AEs. The investigator will exercise his or her medical and scientific judgment in deciding whether an abnormal laboratory finding or other abnormal assessment is clinically significant. Significant abnormal laboratory values occurring during the clinical study will be followed until repeat tests return to normal, stabilize, or are no longer clinically significant. Any abnormal test that is determined to be an error does not require reporting as an AE.

Each AE is to be evaluated for duration, severity, seriousness, and causal relationship to the investigational drug. For each AE, the following information will be recorded:

- Description of the event (eg, headache)
- Date of onset
- Date of resolution (or that the event is continuing)
- Action taken as a result of the event
- Seriousness of the event

- Severity of the event
- Outcome of the event
- Investigator's assessment of relationship to study drug

A cluster of signs and symptoms that results from a single cause should be reported as a single AE (eg, fever, elevated WBC, cough, abnormal chest x-ray, etc, can all be reported as "pneumonia").

The investigator will carefully evaluate the comments of the patient and the response to treatment in order that he/she may judge the true nature and severity of the AE. The question of the relationship of AEs to study drug administration should be determined by the investigator or study physician after thorough consideration of all facts that are available.

Additional information will be collected regarding muscle-related AEs that may include, but may not necessarily be limited to, a muscle-related questionnaire, with questions regarding type of muscle-related symptoms, location of the muscle-related AE, and potential cause of the muscle-related AE.

11.2.4. Severity

It is the investigator's responsibility to assess the intensity (severity) of an AE.

The severity of the AE will be characterized as mild, moderate, or severe according to the following definitions:

- Mild: Events are usually transient and do not interfere with the patient's daily activities
- Moderate: Events introduce a low level of inconvenience or concern to the patient and may interfere with daily activities
- Severe: Events interrupt the patient's usual daily activity, are incapacitating with inability to do usual activities, or significantly affect clinical status and warrant intervention and/or close follow-up

Note: A severe AE need not be serious and an SAE need not, by definition, be severe.

11.2.5. Relationship

It is the investigator's responsibility to assess the relationship of the AE to both the IMP and ezetimibe. The degree of "relatedness" of the AE to the IMP and ezetimibe should be described using the following scale:

- Not Related: No temporal association and other etiologies are likely the cause.
- Unlikely: While cannot be definitively ruled as not related to IMP, a causal association is remote, and other etiologies are more likely to be the cause. For reporting and summarization, events assessed as "Unlikely" to be related to IMP will be considered as "Not Related" to IMP for regulatory reporting purposes.
- Possible: Temporal association, but other etiologies are likely the cause. However, involvement of the study drug cannot be excluded.

- Probable: Temporal association, other etiologies are possible but unlikely. The event may respond if the study drug is discontinued.
- Definite: Established temporal association with administration of the study drug with no other more probable cause. Typically, the event should resolve when the study drug is discontinued and recur on re-challenge.

11.2.6. Monitoring and Follow-up of Adverse Events

Patients having AEs will be monitored with relevant clinical assessments and laboratory tests, as determined by the investigator. All follow-up results are to be reported to the Sponsor personnel or the authorized Medical Monitor. Any actions taken and follow up results must be recorded either on the appropriate page of the eCRF or in appropriate follow-up written correspondence, as well as in the patient's source documentation. Follow-up laboratory results should be filed with the patient's source documentation.

For all AEs that require the patient to be discontinued from the study, relevant clinical assessments and laboratory tests must be repeated at appropriate intervals until final resolution, stabilization of the event(s), or until the patient is lost to follow-up or dies.

Patients with AEs that are ongoing at study completion or study withdrawal must be followed until resolution or for 30 days after the last study visit, whichever comes first (see [Section 11.3](#)).

11.2.7. Treatment-Emergent Adverse Events

TEAE are defined as AEs that begin or worsen after the first dose of study drug.

11.2.7.1. Definition of Serious Adverse Event

An SAE is defined as any AE occurring at any dose that results in any of the following outcomes:

- Results in death
- Is life threatening
- Requires in-patient hospitalization or prolongation of existing hospitalization
- Results in persistent or significant disability/incapacity, or substantial disruption of the ability to conduct normal life functions
- Is a congenital anomaly/birth defect
- An important medical event

Note: Hospitalization is defined as a formal inpatient admission. This will not include admissions under "23-hour Observational Status", an emergency room visit without hospital admission, or an urgent care visit and therefore such events will not be recorded as an SAE under this criterion, nor will hospitalization for an elective or outpatient procedure scheduled or planned before signing of informed consent. However, unexpected complications and/or prolongation of hospitalization that occur during elective or outpatient surgery should be recorded as AEs and assessed for seriousness. Admission to the hospital for social or situational

reasons (eg, no place to stay, live too far away to come for hospital visits) will not be considered inpatient hospitalizations.

Important medical events that may not result in death, be life threatening, or require hospitalization may be considered an SAE when, based upon appropriate medical judgment, they may jeopardize the patient and may require medical or surgical intervention to prevent one of the outcomes listed in this definition. Examples of such medical events include allergic bronchospasm requiring intensive treatment in an emergency room, blood dyscrasias, convulsions that do not result in inpatient hospitalization, or the development of drug dependency or drug abuse.

Any clinical endpoints that meet SAE criteria will be also reported as SAEs. The CEC will adjudicate clinical endpoints in a blinded fashion, but the DMC will review clinical endpoints and SAEs in an unblinded fashion.

11.2.7.2. Definition of Serious Adverse Events or Outcomes not Qualifying as Serious Adverse Events

The following are not considered SAEs and therefore do not need to be reported as such:

- Preplanned or elective hospitalization including social and/or convenience situations (eg, due to inclement weather)
- Overdose of either Esperion study drug or concomitant medication unless the event meets SAE criteria (eg, hospitalization). However, the event should still be captured as a nonserious AE on the appropriate eCRF page

11.2.7.3. Clinical Laboratory Assessments as Adverse Events and Serious Adverse Events

It is the responsibility of the investigator to assess the clinical significance of all abnormal values as defined by the list of reference ranges from the local laboratory. In some cases, significant changes in lab values within the normal range will require similar judgment.

11.3. Reporting Serious Adverse Events

All SAEs, regardless of relationship to study drug, occurring from the time of informed consent until 30 days following the last dose of IMP (for most patients 30 days following their Week 12 visit), must be reported by the principal investigator or designee to the authorized safety designee within 24 hours of the principal investigator or the clinical site becoming aware of the occurrence. All SAEs that the investigator considers related to study drug that occur after the 30-day follow-up of the study period must be reported to the Sponsor.

To report the SAE, complete the provided SAE form and submit it to the safety designee within 24 hours of becoming aware of the occurrence.

The investigator is required to submit SAE reports to the IRB/IEC in accordance with local requirements. All investigators involved in studies using the same investigational product will receive any safety alert notifications for onward submission to their local IRB as required. All reports sent to investigators will be blinded.

All SAEs should be recorded on the eCRF and source documents. Criteria for documenting the relationship to study drug and severity will be the same as those previously described.

The investigator must continue to follow the patient until the SAE has subsided or until the condition becomes chronic in nature, stabilizes (in the case of persistent impairment), or the patient dies.

Within 24 hours of receipt of follow-up information, the investigator must update the SAE form and submit any supporting documentation (eg, patient discharge summary or autopsy reports) to the safety designee.

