10.2.7. Treatment Week 12/EOS (Visit T4; Day 85 ±3 days)

Patients will undergo the following assessments and procedures at Week 12 (Visit T4) when completing an EOS visit or withdrawing from study (early withdrawal).

Patients will undergo the following assessments and procedures at Visit T4:

- Concomitant and prohibited medication review (ongoing)
- Assess AEs, SAEs and potential clinical endpoints
- Physical Exam
- Weight (kg)
- 12-lead ECG
- Vital Signs
- Clinical safety laboratory evaluations (hematology, blood chemistry, and urinalysis)
- Basic fasting lipids (TC, calculated LDL-C, HDL-C, non-HDL-C, and TG)
- Special fasting lipids and other biomarkers (including apoB and hs-CRP)
- HbA_{1C}
- PK sample prior to dose
- Conduct diet and exercise counseling
- Drug return and recording of drug compliance

- Complete study status in IWRS (ie, early withdrawal or completed study).

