10.3. Subject Withdrawal Criteria

10.3.1. Early Withdrawal from the Study

Patients must remain in the study until the last scheduled visit at Week 12 (Visit T4) to be considered as having completed participation in the study.

Patients who withdraw from IMP and/or ezetimibe prior to Week 12 (Visit T4) for any reason will be asked to continue to be followed for safety assessments, including basic fasting lipids, at clinic visit following the protocol-specified visit schedule (see [Appendix 1](#)).

Patients who temporarily withdraw from IMP and/or ezetimibe prior to Week 12 (Visit T4) for any reason may restart IMP and/or ezetimibe providing that (1) the patient and the investigator are in agreement regarding this course of action, (2) the patient has been off of IMP for 4 weeks or less; and (3) IMP can be started as soon as possible. For cases where the patient has been off of IMP for more than 4 weeks, the investigator must contact the medical monitor for approval prior to restarting IMP.

Patients who refuse to continue to return to the clinic for safety assessments will be asked to participate in phone calls from the site at protocol-specified visits (see [Appendix 1](#)), or at a minimum at 12 weeks, to collect information on AEs, concomitant medications, and current health status.

The patient's decision to participate in the clinical study is voluntary. Patients may refuse to continue in the study and/or withdraw from participation in this study at any time, for any reason, specified or unspecified, and without penalty or loss of benefits to which the patient is otherwise entitled.

It is the right and duty of the investigator to interrupt the treatment of any patient whose health or well-being may be threatened by continuation in this study. Such patients should be withdrawn from the study and should not be continued under a modified regimen.

Patients who are withdrawn from the study may not re-enter. The reasons for withdrawal from this study may include:

- Patient's withdrawal of consent
- Failure to comply with the protocol
- Lost to follow-up
- Illness, condition, or procedural complication (including AEs) affecting the patient's ability to participate or requiring prohibited medication
- The Sponsor or investigator terminates the study
- In the investigator's judgment, it is deemed in the best interest of the patient to discontinue his/her participation in the study
- Any other reason

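### Sections 11.3 and 11.2.3 end the reporting of all SAEs on different dates, which separate for patients who stop IMP early but stay on the visit schedule

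*Protocol*

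**What the plan says.** Section 11.3 requires reporting within 24 hours of "All SAEs, regardless of relationship to study drug, occurring from the time of informed consent until 30 days following the last dose of IMP". A parenthesis there treats this date as equal to 30 days after the Week 12 visit, but only for the majority of patients. The section then narrows later reporting to SAEs the investigator considers "related to study drug that occur after the 30-day follow-up of the study period must be reported to the Sponsor".

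Section 11.2.3 says "Any SAE that occurs within 30 days following the last study visit should be reported to the Sponsor", and refers to Section 11.3. The sentence before it uses the other starting point: "Patients should be instructed to report any AE that they experience through 30 days following the last dose of IMP to the investigator".

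Two neighbouring sections count from the end of participation rather than from the last dose. Section 11.2.6 follows ongoing AEs for up to 30 days after the last visit. Section 11.3.2 covers deaths in the 30 days after study completion.

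Section 10.3.1 states that patients who withdraw from IMP or ezetimibe before Week 12 "for any reason will be asked to continue to be followed for safety assessments, including basic fasting lipids", on the normal visit schedule. Sections 11.1.6.3.1 to 11.1.6.3.4 and 11.1.6.3.6 ask the same of patients taken off IMP for liver, renal, hemoglobin, CK or triglyceride findings.

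**The concern.** One obligation, reporting every SAE whatever its cause, has two end dates in current body text. The reference from 11.2.3 to 11.3 can be read as pointing to the procedure only. Even so, 11.2.3 states its own window, and the section it points to states a shorter one for anyone who stops IMP early.

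The amendment history suggests an editing slip. Appendix 5 shows that Amendment 2 added the last-visit sentence to 11.2.3 and, in the same amendment, moved the end date in 11.3 to the last dose. This is offered only as a likely origin. The conflict rests on the current text.

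The consequence is that two sites can each follow the protocol and handle the same event differently. In addition, the instruction given to the patient can lapse before the 11.2.3 window closes, at a time when no further visit is scheduled. The patients concerned include those who stopped IMP for a safety reason.

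**Working it through.** **Inputs.** Week 12 visit (T4) on Day 85 ±3 (Section 10.2.7). Week 4 and Week 8 visits on Days 29 and 57 (Sections 10.2.5 and 10.2.6), used as example days of last dose. Both windows are 30 days. Let D be the day of last dose and V the day of last visit.

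**Formulas.**
- The 11.3 window and the patient's instruction close on D + 30.
- The 11.2.3 window closes on V + 30.
- Gap = (V + 30) − (D + 30) = V − D.
- Part of the gap before the last visit = max(0, V − (D + 30)).
- Part after the last visit = min(30, V − D).

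**The protocol's own equivalence first.** For a completer with V = 85 and D = 84, 11.3 closes on Day 114 and 11.2.3 on Day 115, a gap of 1 day. With D = 85 both close on Day 115. The parenthesis in 11.3 is therefore right for completers.

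**Patients who stop IMP early and attend T4 on Day 85.**

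| Last dose | 11.3 closes | 11.2.3 closes | Gap (days) | Before last visit | After last visit |
|---|---|---|---|---|---|
| Day 57 | 87 | 115 | 28 | 0 | 28 |
| Day 29 | 59 | 115 | 56 | 26 | 30 |
| Day 1 | 31 | 115 | 84 | 54 | 30 |

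Over the T4 window (Day 82 to 88) the gap is 25 to 31 days for a last dose on Day 57 and 53 to 59 days for Day 29. The 11.3 window closes before the last visit only if D + 30 < V, that is, for a last dose before Day 55 when V = 85. The Day 1 row is an extreme: one dose, then full attendance.

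**A worked case.** Last dose Day 57, last visit Day 85, a non-fatal SAE judged unrelated on Day 100.
- 11.2.3: 100 − 85 = 15 days after the last visit, so reportable.
- 11.3, first sentence: 100 − 57 = 43 days after the last dose, so outside the mandatory window.
- 11.3, later-events sentence: does not apply, because the event is judged unrelated.
- Patient's instruction: ended on Day 87.

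**The case against.** The strongest reply is that both sentences can be obeyed. Section 11.3 says what must be reported up to one date and does not forbid reporting later events. A site that follows the wider sentence breaches neither. That is correct, but a site that follows 11.3 alone can also believe that it complies.

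A reader might infer that SAEs go uncollected while early stoppers are still attending visits. The documents do not support this. The first sentence of 11.2.3 collects all AEs, and the section records seriousness for each, from consent to study completion or discontinuation. SAEs are assessed at each visit (at T4, "Assess AEs, SAEs and potential clinical endpoints"). Section 11.3 puts all SAEs on the eCRF, and its form instruction, "complete the provided SAE form and submit it to the safety designee within 24 hours of becoming aware of the occurrence", carries no end date. Section 15.1 also has the investigator inform the ethics committee of all SAEs. During attendance, only the formal application of the mandatory 24-hour route is in doubt.

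A reader might also count a third starting point in the later-events sentence of 11.3. Its follow-up of the study period is most naturally study end plus 30 days, which agrees with 11.2.6, 11.3.2 and the last-visit sentence of 11.2.3. The last-dose date in 11.3 and in the patient's instruction is the outlier.

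After the last visit, what remains is narrow. Deaths are covered by 11.3.2, and related SAEs stay reportable. For clinical endpoints, "Any clinical endpoints that meet SAE criteria will be also reported as SAEs". What is left is new, non-fatal, non-endpoint SAEs judged unrelated, in patients who have been off IMP for some time.

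**Conclusion.** The conflict is real and limited. Completers are affected by about 1 day. Patients who stop IMP early and stay on the schedule have two end dates that differ by V − D, for example 28 or 56 days with T4 on Day 85. Patients who leave the study altogether and have a prompt end-of-study visit are little affected.

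Two things are uncertain: whether the mandatory 24-hour route for all SAEs runs past 30 days after the last dose, and whether the residual events described above are learned of and reported in the 30 days after the last visit. No efficacy endpoint is touched.

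The day counts assume nominal visit days except where the T4 window is shown. The protocol gives no early-stop rate, so the number of patients concerned is unknown. The passages are wrong as written and should be reconciled before sites rely on them.

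**What to change.** Reconcile Sections 11.2.3 and 11.3 to one stated end date for reporting all SAEs regardless of relationship. Start the related-only rule in 11.3 on the day that window ends. Align the patient's instruction for serious events in 11.2.3 to the same date. The choice of date is the sponsor's; as an illustration, ending at the later of the two current dates would satisfy both existing sentences. The collection of non-serious AEs need not change.

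The cost is amendment wording in two sections and possibly a few more SAE forms.
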